## STUDY PROTOCOL

### 1. Scientific background

Random-start ovarian stimulation (OS) cycles have been well described in oncologic patients for female fertility preservation. In this scenario, (usually) young women have initiated ovarian stimulation independently of the menstrual cycle following an specific ovarian stimulation protocol (1).

Recently, Kuang *et al.* (2) showed that it was feasible to perform a “luteal phase” stimulation or even two consecutive ovarian stimulations in the same cycles (the so-called “DUOSTIM” protocol). This “luteal” phase stimulation protocol has been also described in egg-donors in a pilot trial (3). Importantly, in egg-donors, luteal phase stimulation seems to provide competent eggs.

The physiologic fundamentals for the optimal results in these “non-conventional” stimulation protocol is derived from the “follicular waves” theory described by Baerwald *et. al.* (4).

Of notice, random-start stimulation protocols initiating in the mid/to late follicular phase have been essentially in the oncologic population and, so far, optimal results are described (5-6). The same optimal results have been also described in luteal phase stimulation protocols, nonetheless, at least one study has related luteal phase stimulation protocol with suboptimal results in terms of pregnancy achievement (7).

The current trial aims to explore the concept of random-start stimulation protocols, namely, initiating ovarian stimulation on the mid/late follicular and luteal phase and to compare the results versus conventional stimulation protocols initiating OS in the early follicular phase in the egg-donor population. This approach might facilitate schedules in egg-donor IVF programs.

### 2. Methods

#### 2.1 Design

This is a prospective, open, randomized, self-comparative, pilot study. The type of protocol (antagonist/GnRH-a trigger) and gonadotrophin type/dose will be identical between the study and control groups; except for the day of starting the OS process in relation to the last menses. The control cycle includes a conventional previous cycle underwent by the same population in the six previous months of the randomization, thereby, decreasing inter-subject variability. The eggs from the study group will be

inseminated using IVF conventional / ICSI using partner's sperm. Fertilization will be evaluated 18-24 hours later.

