## 2.2 Study population

### a) Inclusion criteria:

- Egg-donors having at least one previous ovarian stimulation for egg-donation in our institution within the six months before being enrolled in the current trial.
- Regular cycles 27 +- 7 days
- Written / signed informed consent.

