## 2.4 Statistical analysis plan and sample size

The sample size was calculated assuming a non-inferiority margin of 5 eggs SD 6.7 (based on: Devroey et al. Hum Reprod. 2009;24(12):3063-72). A unilateral alpha level of 0.05 was established. With the aim to show that the difference in the mean number of collected eggs will not exceed 5, a statistical power of 80% required 30 patients per group (1:1 allocation, total sample: 60). Statistical analysis was performed using t-student test for continuous variables and chi-square test for categorical parameters. A P value of <.05 was considered significant.

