### STUDY GROUP:

Visit:	Schedule	Investigation:
Start of treatment (S1)	Beginning of gonadotrophins administration (according to randomization): 
 
- 5o day of the cycle
 
- 7o day of the cycle
 
- 9o day of the cycle
 
- 11o day of the cycle
 
- 13o day of the cycle
 
	
 
• Starting dose: identical to the dose used in the control cycle.
 
• S1 refers to the first day of ovarian stimulation
 

Visit 2 (1st control)	On the 5 o -6 o of ovarian stimulation (S5-S6)	
 
• Transvaginal scan and folliculometry
 
• Starting of GnRH antagonist (Cetrotide® )
 
• Blood samples: Estradiol, Progesterone, FSH, LH
 

Follow-up	Every 24-72 hours	
 
• Transvaginal scan and folliculometry
 

Visit 3 (Agonist)	On the day of triggering (final follicular maturation)	
 
• Transvaginal scan and folliculometry
 
• Administration of 2 ampules of Decapeptyl® (0,2 mg triptorelin acetate) with follicles 18-20 mm.
 

Visit 4 (Egg collection)	Egg collection	
 
• Transvaginal egg retrieval 36 hours after triggering.
 
• Blood samples: Estradiol, Progesterone, FSH, LH.
 

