### CONTROL GROUP:

A previous cycle underwent by the egg-donor within 6 months previously to the inclusion in the study group for the ROSE trial; in brief:

- Day 1-2 of the cycle. Transvaginal scan and follicular count. Starting of gonadotrophins 150-225 IU (Fostipur®) according to BMI and AFC (D1 of ovarian stimulation).
- Day 5-6 of ovarian stimulation. Transvaginal scan and folliculometry. Starting of GnRH antagonists (Cetrotide®) beginning with a dominant follicle  $\geq 14$  mm.
- Follow-up every 24-72 hours.
- Administration of 2 ampules of Decapeptyl® (0,2 mg triptorelin acetate) with follicles 18-20 mm to induce the final follicular maturation.
- Transvaginal egg retrieval 36 hours after triggering

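### Randomisation assigns only the start day; study versus control is a non-randomised comparison with the donor's earlier cycle, so 1:1 allocation is wrong and order is confounded with start timing

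*Combined protocol and SAP*

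**What the plan says.** Section 2.1 gives the design label: "This is a prospective, open, randomized, self-comparative, pilot study". It then defines the comparator: "The control cycle includes a conventional previous cycle underwent by the same population in the six previous months of the randomization". The reason given is lower variability between subjects.

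The Control group section repeats the definition: "A previous cycle underwent by the egg-donor within 6 months previously to the inclusion in the study group for the ROSE trial". That cycle starts conventionally: "Day 1-2 of the cycle. Transvaginal scan and follicular count". The inclusion criteria make an earlier stimulation a condition of entry: "Egg-donors having at least one previous ovarian stimulation for egg-donation in our institution within the six months before being enrolled".

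The study overview places randomisation at Visit 1. The Study group table shows what it decides: "Beginning of gonadotrophins administration (according to randomization"), followed by five options, days 5, 7, 9, 11 and 13. The conventional day 1-2 start is not among them.

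Section 2.4 sizes the trial as "30 patients per group (1:1 allocation, total sample: 60"), with a margin of 5 eggs, SD 6.7, one-sided alpha 0.05 and 80% power. The analysis is a Student t test for continuous variables. Pairing, order and period are not mentioned. The main outcome at the end of the protocol compares the different start moments with the standard protocol.

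**The concern.** Section 2.4 reads as a parallel-group trial in which patients are allocated evenly to two arms. Section 2.1 and the Control group section describe one set of donors, each compared with her own earlier cycle. Both cannot be right, and it is unclear whether 60 counts people or cycles.

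The interpretation of the main result depends on this. In every donor the conventional cycle comes before the study cycle. A difference between repeated stimulations, or between calendar periods, falls entirely on the study side of the comparison. Using the donor as her own control removes variation between donors, which helps precision but does not remove an order effect. A non-inferiority statement could then be read as having the protection of randomisation, which this comparison lacks.

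**Working it through.** **What is randomised**

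| Contrast | How donors reach each side | Order of cycles |
|---|---|---|
| Start day 5 v 7 v 9 v 11 v 13 | Randomised at Visit 1 | Same in all five groups (control, then study) |
| Any study start v conventional start | Every donor supplies both; none is allocated | Always control first |

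For the second row, mean(study - control) = start-timing effect + order or calendar effect. With a single order, the data cannot separate the two terms. In the first row the order effect is common to all groups and cancels.

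**The plan's own figure**

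For two independent groups with no true difference, n per group = 2(z₁₋α + z₁₋β)² SD² / margin².

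- One-sided 0.05, 80% power: 2 × (1.645 + 0.842)² × 6.7² / 5² = 22.2, so 23 per group. The stated 30 is not reproduced.
- One-sided 0.025, 80% power: 2 × (1.960 + 0.842)² × 6.7² / 5² = 28.2, so 29 (30 with the t distribution), which matches.

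The stated 30 is therefore conservative at one-sided 0.05, and this discrepancy does not bear on the present point. It does show that the calculation was for independent groups.

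**What a drift would do**

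From section 2.4: margin 5, SD 6.7, one-sided alpha 0.05, and 30 taken as the number of pairs. Assumed, because the documents give no values: a drift of 1 or 2 eggs between cycles, and a within-donor correlation r from 0 to 0.7.

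SD of the difference = 6.7 × √(2(1 - r)), and SE = that / √30. At r = 0.5, SD = 6.7 and SE = 1.22 eggs. If the true loss is exactly 5 eggs and the later cycle gains s eggs for order reasons alone, the paired test statistic follows a noncentral t on 29 degrees of freedom with noncentrality s/SE. Its critical value is 1.699.

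| r | SE | False non-inferiority, s = 0 | s = 1 | s = 2 |
|---|---|---|---|---|
| 0 | 1.73 | 5% | 14.0% | 30.3% |
| 0.3 | 1.45 | 5% | 16.6% | 38.4% |
| 0.5 | 1.22 | 5% | 19.9% | 48.1% |
| 0.7 | 0.95 | 5% | 27.0% | 66.1% |

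Drift the other way costs power. With no true difference, noncentrality is (5 - 2)/SE for a 2-egg fall. Power drops from 88-100% without drift to 52-93% over the same range of r.

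**If the t test is unpaired**

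Section 2.4 does not rule this out. The test would use SE = 6.7 × √(2/30) = 1.73 and require an excess over -5 of 1.672 × 1.73 = 2.89 eggs. At r = 0.5 the true SE is 1.22, so the normal approximation gives tail points of:

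- no drift: 2.89/1.22 = 2.36
- 1 egg: 1.89/1.22 = 1.55
- 2 eggs: 0.89/1.22 = 0.73

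Simulation of the t test gives rates of about 1%, 7% and 24%. These are lower than for the paired test because the unpaired test is conservative under positive correlation. The drift acts in the same direction.

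**Tipping point, for illustration**

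The lower limit is d - 1.699 × SE, so the order shift that brings it to -5 is d + 5 - 1.699 × SE. For an observed difference d = 0 and r = 0.5, this is 5 - 1.699 × 1.22 = 2.9 eggs.

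**The case against.** The design is disclosed. Section 2.1 calls the study self-comparative and a pilot, says that the control is a previous cycle and gives a reason. A prior-cycle self-control is a legitimate choice for a pilot. All of that stands, but disclosing the control does not address order confounding, and the pilot label sits beside a formal non-inferiority margin and power statement.

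The numerical illustration is also open to challenge. The drift and correlation are assumed, with no evidence of the drift's size or direction; 1 and 2 eggs are 20% and 40% of the margin. The false-positive rates apply only at a true loss of exactly 5 eggs. The larger rates need a paired test that the plan does not specify. These points stand and limit how the figures may be used. The drift could be zero, but the design cannot show that it is.

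A reader might go further than the documents allow in four ways:

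- **That the study is not randomised at all.** Donors are randomised among five start days, so the label is true for those contrasts.
- **That donors were chosen on their earlier response.** The eligibility criteria contain no response criterion.
- **That the control is the donor's first stimulation.** At least one previous stimulation is required, so the control is an earlier cycle but not necessarily the first.
- **That the sample is 30 donors with two cycles each.** Section 2.4 does not settle whether 60 counts donors or cycles.

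**Conclusion.** The point holds for study versus control. The allocation ratio in section 2.4 describes a feature that the design does not have, and the word randomized in section 2.1 is accurate only for contrasts among start days. The main comparison with the standard protocol is a non-randomised before-after comparison in which order and start timing cannot be separated, and no analysis or stated limitation deals with this.

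The possible size is illustrative. Under the paired assumptions above, an unrecognised gain of 1 egg in the later cycle would raise a 5% error rate roughly three- to fivefold; under an unpaired test at r = 0.5 the rate would be about 7%. Neither figure is evidence that a drift exists. The study can proceed, but its main comparison should not be presented as randomised.

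**What to change.** 1. In sections 2.1 and 2.4, state that randomisation applies to start day only, and that study versus control is a non-randomised comparison with the donor's own prior cycle.
2. In section 2.4, delete the 1:1 allocation and state whether 60 counts donors or cycles. The sponsor must supply this, since the documents do not.
3. Specify a paired test of the within-donor differences for the comparison with the standard protocol.
4. State order and calendar confounding as a limitation. With the result, report the order shift, in eggs, that would move the confidence limit across -5.
5. Optionally, if there are donors with two conventional cycles within the six months, report their change between cycles as a rough guide to the drift. The documents do not show that such donors exist, and they may be few and unrepresentative.

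Items 1 to 4 cost wording and one short calculation, with no new arm or additional donors. The downside is a more cautious non-inferiority claim. These changes make the confounding visible but do not remove it; that would need randomised cycle order or a concurrent conventional-start group, which would be a different study.

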### **Secondary outcomes**

To evaluate differences with regards to the duration of the ovarian stimulation, FSH consumption and fertilization rates between groups.

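### The fertilisation comparison makes no allowance for insemination method or sperm source, either of which may differ between a donor's study and control cycles

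*Combined protocol and SAP*

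**What the plan says.** The last secondary-outcome statement in the protocol overview covers stimulation duration, "FSH consumption and fertilization rates between groups". The secondary list in section 2.3, as it reads, does not name fertilisation.

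Insemination is described once, in section 2.1. The sentence begins "The eggs from the study group will be" and continues "inseminated using IVF conventional / ICSI using partner's sperm". It is followed by "Fertilization will be evaluated 18-24 hours later". No denominator is given (eggs collected, metaphase II eggs or eggs inseminated).

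The control is "A previous cycle underwent by the egg-donor within 6 months previously to the inclusion in the study group". Its description under the control-group heading ends with "Transvaginal egg retrieval 36 hours after triggering", so nothing is said about how those eggs were inseminated or with whose sperm.

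The features held equal are listed in section 2.1: "The type of protocol (antagonist/GnRH-a trigger) and gonadotrophin type/dose will be identical between the study and control groups". Insemination is not among them.

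Section 2.4 assigns the Student t test to continuous variables and the "chi-square test for categorical parameters". It mentions no stratification, covariate, pairing or clustering, and it does not say which test fertilisation will get.

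**The concern.** The design relies on each donor serving as her own control, which removes differences that stay with the donor. Insemination method and sperm source belong to the cycle. The control eggs came from a separate donation, so they may have been inseminated by another method or with other sperm. Randomisation does not help, because it allocates start days within the study group while the control cycle lies in the past.

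At stake is how the secondary result is read. A fertilisation difference produced by the laboratory method could be credited to the start day. Equally, a real reduction after a late start could be hidden by a more favourable method mix in the study cycles. In a trial built to show that late starts are not worse, the second error matters as much as the first.

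**Working it through.** **The plan's own figure.** There is none for fertilisation. The only calculation is for eggs collected (margin 5, SD 6.7, one-sided 0.05, 80% power, 30 per group). The usual formula gives 2 × 6.7² × (1.645 + 0.842)² / 5² = 22.2, so 23 per group. One-sided 0.025 gives 28.2, so 29, or 30 with the t distribution. That mismatch is a separate matter. Only the 30 cycles per condition are used below.

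**Assumed inputs (none is in the documents).** 10 eggs inseminated per cycle, so 300 per condition; ICSI and conventional IVF fertilisation rates as shown; no true effect of start day.

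**Bias from the method mix.** Spurious difference = (ICSI rate − IVF rate) × (ICSI share in study cycles − ICSI share in control cycles). The last column is the approximate probability that a two-sided 5% chi-square on pooled eggs rejects.

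| ICSI share, study vs control | ICSI / IVF rate | Spurious difference | Rejects |
|---|---|---|---|
| 50% vs 50% | any | 0 | 5% |
| 70% vs 50% | 70 / 65% | 0.05 × 0.20 = 1 point | 6% |
| 70% vs 50% | 75 / 65% | 0.10 × 0.20 = 2 points | 8% |
| 70% vs 50% | 75 / 60% | 0.15 × 0.20 = 3 points | 13% |
| 80% vs 20% | 70 / 65% | 0.05 × 0.60 = 3 points | 12% |
| 80% vs 20% | 75 / 65% | 0.10 × 0.60 = 6 points | 36% |
| 80% vs 20% | 75 / 60% | 0.15 × 0.60 = 9 points | 65% |

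The extreme is a complete switch of method with a 20-point method effect: 0.20 × 1.00 = 20 points.

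The spurious difference does not depend on the test. A t test on per-cycle rates would carry the same bias, though the rejection rates above would not apply to it.

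**Scale against sampling error.** At a 70% rate with pooled eggs, SE = √(2 × 0.7 × 0.3 / 300) = 0.037. An artefact of 2.5 points is 0.025 / 0.037 = 0.7 SE and would pass unnoticed. One of 10 points is 2.7 SE.

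**Sperm source with an equal mix.** Sperm that varies independently between cycles has no expected direction. It does make eggs within a cycle alike, which a pooled chi-square ignores. With 10 eggs per cycle the variance is inflated by 1 + 9 × ICC, and the false-positive rate is 2 × [1 − Φ(1.96 / √(1 + 9 × ICC))].

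| ICC | Inflation | False-positive rate |
|---|---|---|
| 0 | 1.00 | 5% |
| 0.05 | 1.45 | 10% |
| 0.10 | 1.90 | 15% |
| 0.20 | 2.80 | 24% |

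A simulation of 20,000 trials per row gave the same rates. Variation in a donor from one cycle to the next acts in the same way. This part applies only if eggs are the unit of analysis.

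**The case against.** The strongest reply is that nothing shows the cycles to differ. A reader might infer that the control eggs did go to another couple, with other sperm or another method. That is plausible in a donation programme, but the documents leave it unstated. Nor does anything suggest that the clinic would choose the method according to start day. If the mix is the same in both cycles, the method bias is zero. This stands, and it limits the point to what the plan leaves open. Even so, a mix that differed only by chance would shift this one trial's result, in a direction nobody could know without the records.

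A reader might also take section 2.4 to prescribe a pooled egg-level chi-square. It does not; a per-cycle rate could go to the t test. The clustering figures and rejection rates are therefore conditional on pooling, while the bias from an unequal mix is not.

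A third tempting reading is that the artefact would be large and nominally significant. A 10-point artefact needs a complete switch of method at a 10-point method effect, or a 50-point share difference at a 20-point effect. The documents support neither.

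Finally, the study is a self-described pilot, and no passage says that fertilisation will be read as evidence on egg competence after a late start. That is fair, and it keeps the weight low. The plan does still commit to comparing fertilisation between groups.

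**Conclusion.** The point holds in a limited form. As written, the plan cannot separate start day from insemination method or sperm source in the fertilisation comparison, and same-donor control does not repair this. An unequal method mix biases the result under either test. Independent variation in sperm source adds noise rather than a directional bias, and it understates the P value if eggs are pooled.

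Neither the size nor the direction can be obtained from the documents. The range from 0 through 1 to 9 points, and up to 20 at the extreme, rests wholly on assumed rates and ICSI shares; the rejection rates also rest on the assumed egg count and egg-level pooling. Only a secondary outcome is touched. Egg number, metaphase II outcomes and the sample size do not depend on it.

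**What to change.** In section 2.4 and the overview's secondary outcomes:

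- Take insemination method and sperm source for both cycles from existing records, and tabulate them by condition.
- Define one fertilisation denominator and use it in both cycles.
- Compare paired donor-level rates among donors whose two cycles used the same method. Alternatively, to keep donors whose method changed, fit a paired or mixed logistic model with method as a covariate and donor and cycle as random effects.
- Report the result as descriptive. State that sperm source may differ between cycles, and make no claim that start day does or does not affect fertilisation.

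The cost is plan wording, a record check and one table, with no extra donors and no change in the laboratory. The price is lower precision, especially if the analysis is restricted to same-method donors, and a weaker secondary claim. Sperm source remains uncontrolled in either version, which is why the descriptive label is needed.

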## 2.2 Study population

### a) Inclusion criteria:

- Egg-donors having at least one previous ovarian stimulation for egg-donation in our institution within the six months before being enrolled in the current trial.
- Regular cycles 27 +- 7 days
- Written / signed informed consent.

### b) Exclusion criteria:

- Ovarian pathology at the moment of initiating COS (e.g ovarian cysts)
- Simultaneous participation in another study.

## 2.3 Objectives

### a) Main outcome

- Total number of collected eggs
- Total number of metaphase II eggs
- Proportion of metaphase II eggs: total number/number of metaphase II

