### **Main outcome**

To evaluate and compare the total number and MII rate of eggs collected after beginning the ovarian stimulation in different moments of the follicular phase vs standard protocol.

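### Three unranked main outcomes share one P<.05 rule, but only collected eggs has a margin, an alpha and a sample size; the plan should name it as the single primary outcome

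*Combined protocol and SAP*

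**What the plan says.** Section 2.3 places three items under its Main outcome heading: "Total number of collected eggs", "Total number of metaphase II eggs" and "Proportion of metaphase II eggs: total number/number of metaphase II". None is marked as leading. The Main outcome statement at the end of the document gives the aim as "To evaluate and compare the total number and MII rate of eggs collected" under different start days versus the standard protocol. That is two items, again unranked.

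Section 2.4 is specific about one outcome only. It assumes "a non-inferiority margin of 5 eggs SD 6.7", adds that "A unilateral alpha level of 0.05 was established", and states the purpose of the calculation: "With the aim to show that the difference in the mean number of collected eggs will not exceed 5". The result is 30 patients per group at 80% power. The section then names the t test and the chi-square test and sets a single P<.05 threshold. That threshold is not limited to any outcome, and its side is not given.

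The documents contain no order of testing, no multiplicity adjustment, no rule on whether one or all main outcomes must succeed, and no margin or power for either MII outcome.

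**The concern.** Two problems follow from the lists and the threshold taken together.

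- **Success is not defined for the set of main outcomes.** Suppose collected eggs meets the margin while MII eggs is significantly lower, or the reverse. The plan does not say whether the trial has succeeded, so that choice could be made after the data are seen. Depending on the choice, either the 5% level is exceeded or power is lost.
- **Two main outcomes cannot serve the stated aim.** The only aim formulated in section 2.4 is non-inferiority, which needs a margin. With no margin, P≥.05 on MII eggs or MII proportion means only that no difference was detected. Nothing in the plan prevents it from being reported as equivalence. This second problem depends on no assumption about correlations or about the success rule.

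**Working it through.** **Inputs.** From section 2.4: margin 5, SD 6.7, one-sided alpha 0.05, power 80%, 30 per group. From section 2.3: three main outcomes. The correlations between the test statistics are my assumptions, because the documents give none.

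**Step 1: the plan's own figure.** For two groups with a true difference of zero, n per group = 2 × [SD × (z_alpha + z_power) / margin]².

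- One-sided 0.05: 2 × [6.7 × (1.645 + 0.842) / 5]² = 22.2, so 23 per group.
- One-sided 0.025: 2 × [6.7 × (1.960 + 0.842) / 5]² = 28.2, so 29 (30 with the t distribution).

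The stated 30 does not follow from the stated one-sided 0.05, but the difference is on the safe side. With 30 per group the standard error is 6.7 × √(2/30) = 1.730 and 5/1.730 = 2.890. Power at one-sided 0.05 is Φ(2.890 − 1.645) = 89%.

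**Step 2: any one outcome counts as success.** The error is the probability that at least one test passes when every null hypothesis holds at its boundary. For three independent one-sided tests it is 1 − 0.95³ = 14.26%. If collected eggs is tested one-sided at 0.05 and the two MII tests are two-sided at 0.05, each MII test has a 2.5% chance of a falsely favourable result, so it is 1 − 0.95 × 0.975² = 9.69%. With equal correlations, from the trivariate normal distribution:

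| Assumed correlation | Three one-sided 0.05 tests | Eggs one-sided, MII tests two-sided |
|---|---|---|
| 0 | 14.26% | 9.69% |
| 0.3 | 13.03% | 9.02% |
| 0.5 | 11.84% | 8.29% |
| 0.8 | 9.26% | 6.65% |

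For the two items in the closing statement, independent and one-sided, the figure is 1 − 0.95² = 9.75%.

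MII count equals collected eggs times MII proportion, so independence is not realistic and the first row is an upper figure. The one-sided column also treats the MII tests as if each had a one-sided null, which the plan never defines. The right-hand column is the reading with ordinary difference tests.

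**Step 3: all three must succeed.** The error is then not inflated. Power for the MII outcomes cannot be derived because they have no margin, so two illustrations follow.

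- If each outcome had exactly the stated 80%, joint power would be 0.80³ = 51% under independence and 72% at correlation 0.9.
- If each had the 89% that 30 per group gives for collected eggs, joint power would be 0.8935³ = 71% under independence and 84% at correlation 0.9.

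In each case joint power is below that of a single outcome.

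**Step 4: collected eggs as sole primary.** Alpha stays at one-sided 0.05 and power is 89% with the planned 30 per group. A Bonferroni split over three (0.05/3 = 0.0167) would give 77.7% power for collected eggs at 30 per group and would need 32 per group for 80%.

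**The case against.** The strongest reply is that section 2.4 already shows which outcome leads. Collected eggs is the only outcome with a margin, an alpha and a sample size, and it is listed first in both places. This stands in part. A reader might infer that the trial has no success criterion or error rate at all, and the documents do not support that: for collected eggs both are given, and a claim on that outcome alone keeps its 5%. What no section says is that the other main outcomes rank below it.

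A reader might also infer that the plan allows success on any of the three, so that its error rate is simply 14%. The documents do not support that either. No section states such a rule, the side of the P<.05 threshold is not given, and 14% needs one-sided, independent tests. The inflation is conditional.

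The difference between the two lists is minor, since egg number and MII rate together imply the MII count. A fixed testing order would also hold 5%, but each MII outcome would then need its own margin or stated hypothesis. Finally, section 2.1 calls this a pilot study. That lowers the stakes, yet section 2.4 still sets a margin, an alpha, a power and a significance threshold.

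**Conclusion.** The concern holds in a conditional form. The plan defines a criterion and a 5% level for collected eggs only, and leaves the role of the two MII outcomes open. Under an any-one rule the false-success rate exceeds 5%: about 9–14% with one-sided tests, or about 7–10% with two-sided MII tests, for assumed correlations from 0.8 to 0. Under an all-three rule the cost is power instead, and its size cannot be fixed without MII margins. The conclusion that needs no assumption is that the MII outcomes, as planned, cannot support non-inferiority or a claim of no difference. This should be corrected, but it does not invalidate the analysis of collected eggs.

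**What to change.** - **Section 2.3 and the closing Main outcome statement:** name total collected eggs as the single primary outcome, to match section 2.4. Make MII count and MII proportion key secondary outcomes, reported with confidence intervals and with no non-inferiority or no-difference claim.
- **Section 2.4:** limit the one-sided 0.05 confirmatory test to the primary outcome, judged against the margin of 5.
- **Section 2.3, same edit:** correct the inverted ratio to number of MII eggs divided by total number. As written it cannot be below 1, so it is not a proportion.

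The cost is wording only, with no extra donors or procedures. The one downside is that the MII outcomes lose their main status.

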### B) Secondary outcomes

- To evaluate the total number of days for COS
- 
- To evaluate the amount of gonadotrophin consumption (IU)

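### The proportion of mature eggs is written upside down, and the analysis rule gives neither a unit of analysis nor pairing by donor

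*Combined protocol and SAP*

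**What the plan says.** Section 2.3 lists three main outcomes: eggs collected, metaphase II (MII) eggs, and a third defined as "Proportion of metaphase II eggs: total number/number of metaphase II". This is the only formula given for it. The Main outcome paragraph at the end of the protocol restates the aim, "To evaluate and compare the total number and MII rate of eggs collected", without a formula.

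The whole test specification is one sentence in section 2.4: "Statistical analysis was performed using t-student test for continuous variables and chi-square test for categorical parameters". The sample size in the same section is worded as two groups of 30 with 1:1 allocation, 60 in total.

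The design is self-comparative. Section 2.1 describes the control cycle as "underwent by the same population in the six previous months of the randomization, thereby, decreasing inter-subject variability". The Control group section confirms it: "A previous cycle underwent by the egg-donor within 6 months previously to the inclusion in the study group". The Study group table sets the starting dose as "identical to the dose used in the control cycle".

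**The concern.** There are two linked faults.

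**Definition.** Followed literally, the third main outcome is total over MII. It moves in the opposite direction to the MII rate that the trial sets out to compare, and it is undefined for a donor with no mature egg.

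**Analysis.** The rule in section 2.4 does not assign the MII proportion to either test and does not name its unit. It leaves room for a chi-square test on pooled eggs, which treats eggs from one retrieval as independent, or for an unpaired t test on donor values, which ignores that each donor appears in both arms. The missing word on pairing affects every comparison between the two cycles: collected eggs, MII count, stimulation days and gonadotrophin IU, as well as maturity. The reduction in inter-subject variability that section 2.1 offers as the reason for the design is obtained only if the analysis uses the pairing.

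At stake are a misdefined main outcome, and a choice between tests with quite different error rates that could be made after the data are seen.

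**Working it through.** **1. The formula.** Let M be the MII eggs and T the total eggs in one donor-cycle. The proportion is M/T; the plan writes T/M.

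- T = 12, M = 9: 12/9 = 1.33 as written, against 9/12 = 0.75.
- T = 12, M = 6: 12/6 = 2.0 as written, against 0.50.
- Inverting a group mean afterwards does not repair it. Two donors with 12/12 and 6/12 mature average (1.0 + 2.0)/2 = 1.50 as written, whose inverse is 0.67. Their mean MII rate is (1.00 + 0.50)/2 = 0.75.

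**2. The plan's own sample size.** Section 2.4 gives a margin of 5 eggs, SD 6.7, one-sided alpha 0.05 and 80% power. For two independent groups, n = 2(1.645 + 0.842)² × 6.7²/5² = 22.2, so 23 per group, not 30. With 1.960 in place of 1.645 the formula gives 29, and the exact t calculation gives 30. The present point does not depend on this discrepancy. It does show that the stated figure is not a paired calculation: none of these formulas contains a within-donor correlation.

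**3. Maturity: type I error of the tests the rule allows.** SD 6.7 and n = 30 come from section 2.4; reading n = 30 as 30 donors with two cycles each is an interpretation. Assumed: mean 10 or 15 eggs, 75% mature, egg correlation within a cycle 0.044 or 0.102, and no true difference. There were 10,000 simulated trials per setting, at two-sided 0.05. Ranges run over the four combinations.

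| Share of clustering at cycle level | Pooled egg chi-square | Unpaired t, donor values |
|---|---|---|
| 0% (stable donor effect) | 5-7% | 0.4-2.7% |
| 20% | 7-10% | 0.9-3.3% |
| 50% | 9-16% | 2.1-3.8% |
| 100% | 12-24% | about 5% |

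The paired t test on donor proportions holds 4.5-5.4% in every row.

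The bottom row can be checked by hand. Pooling inflates the variance by about 1 + (w - 1) × ICC, where w = mean + SD²/mean. For mean 15, w = 15 + 44.89/15 = 18.0. With ICC 0.044 the factor is 1.75, and 1.96/√1.75 = 1.48 has a two-sided tail of 13.8% (simulated 14.0%). With ICC 0.102 the factor is 2.73, and the tail is 23.6% (simulated 23.8%). In the top row most of the inflation disappears because a stable donor effect is present in both cycles and largely cancels.

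With 60 donors instead of 30, chi-square size is 5.3-6.8% in the top row and 12.0-23.3% in the bottom row.

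**4. Collected eggs.** Margin, SD and one-sided alpha come from section 2.4; 30 pairs, with within-donor correlation ρ assumed. The standard error of the difference is 6.7 × √(2/30) = 1.730 unpaired and 1.730 × √(1 - ρ) paired. The 95% half-widths use t = 2.002 (58 df) and t = 2.045 (29 df). Size and power come from 100,000 simulated trials.

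| ρ | Size at the margin, unpaired | Power, unpaired | Power, paired | 95% half-width, unpaired | 95% half-width, paired |
|---|---|---|---|---|---|
| 0 | 5.0% | 89% | 88% | 3.46 | 3.54 |
| 0.2 | 3.3% | 91% | 93% | 3.46 | 3.16 |
| 0.4 | 1.8% | 94% | 98% | 3.46 | 2.74 |
| 0.6 | 0.6% | 97% | 99.8% | 3.46 | 2.24 |

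Paired size is 4.9-5.0% throughout.

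**The case against.** The best defence is that the plan specifies no wrong test. The inverted formula is probably a slip: its own label says proportion, the closing Main outcome paragraph says MII rate, and a value above 1 would be noticed. Student's t test includes the paired form, and the self-comparative design points to it. The largest error rates require that a donor's maturity rate has no stable component, which sits badly with the reason for using her as her own control. For collected eggs, the only powered outcome, an unpaired test never exceeds its nominal size and keeps more than 80% power. The study is labelled a pilot.

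Much of this is right. The second fault is an omission rather than a wrong choice, the top of the chi-square range is an extreme setting, and the harm for collected eggs is small. But no section gives the correct formula, so the inverted one is the operative definition of a main outcome. The two-group wording of section 2.4 also makes unpaired tests a reasonable reading of the plan.

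Two further objections concern what pairing requires. Section 2.2 admits donors with one or more qualifying earlier cycles, so the control cycle may not be unique. The corrected proportion is itself undefined if no egg is collected; the simulation set a minimum of one egg. Both are fair. Neither weakens the case for correcting the plan.

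**Conclusion.** The concern holds and should be fixed. That the formula is the reciprocal of the outcome it names, and that unit and pairing are unstated, can be read directly from the documents.

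The consequence is less certain. For maturity, the two permissible misreadings do harm in opposite settings: pooling eggs is worst when clustering lies within cycles, and an unpaired t test is most conservative when it is a stable donor effect. The documents give neither the egg correlation nor its split between donor and cycle, so the true size cannot be fixed within the ranges shown. For collected eggs the error is in the conservative direction only, a modest loss of power and precision that grows with the within-donor correlation.

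**What to change.** - **Section 2.3:** define the third main outcome, per donor-cycle, as MII eggs divided by total eggs collected.
- **Section 2.4:** state that this outcome is compared by a paired analysis of donor-level proportions, or by a logistic GEE or mixed model on eggs that accounts for donor and cycle, and not by an egg-level chi-square or an unpaired t test. State that the t tests on collected eggs, MII count, stimulation days and gonadotrophin IU are paired by donor.
- **While editing:** say which earlier cycle is the control if several qualify, and how a cycle with no eggs is handled.

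Fertilisation rate is outside this change, because the documents do not describe insemination of control-cycle eggs.

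The cost is one corrected line and a sentence or two of analysis text, with no new data. Intervals for maturity may be wider than those from pooled eggs. If a donor's two cycles are uncorrelated, pairing costs about 1 percentage point of power on collected eggs (88% against 89%).
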